## 6.0 CRITERIA FOR PARTICIPANT ELIGIBILITY

### 6.1 Participant Inclusion Criteria

- Patients must have pathologically or cytologically confirmed solid or hematologic cancers.  
OR
- Patient is receiving alpelisib for PIK3CA-Related Overgrowth Spectrum disorder.
- Female and male aged 18 to 85 years, inclusively, at the time of Week 0/Day 1 of treatment.
- Patients must have a therapy-related CTCAE grade 2/3 (See Appendix A) cutaneous adverse event defined as any cutaneous reaction listed below and blood eosinophil counts of at least .3 K/mcl.
  - Rash maculo-papular
  - Bullous dermatitis
  - Pruritus
  - Urticaria
  - Eczema
- Patients must plan to continue on culprit drugs (cancer patients).
- Patients planning to receive alpelisib indicated for PIK3CA-Related Overgrowth Spectrum disorder OR patients receiving immunotherapy and/or targeted therapy, including but not limited to the following agents, will be eligible for inclusion:
  - Immunotherapies: ipilimumab, nivolumab, pembrolizumab, avelumab, durvalumab, atezolizumab, tremelimumab.
  - Targeted therapies: trastuzumab, pertuzumab, alpelisib, osimertinib, everolimus, temsirolimus, sorafenib, regorafenib.
- Patients using topicals/orals for indication of skin rash/pruritus for at least 7 days should continue using these drugs for the study duration.
- Adequate bone marrow, liver and renal function:
  - Total bilirubin  $\leq$  1.5 x the upper limit of normal (ULN)
  - Alanine aminotransferase (ALT) and aspartate amino-transferase (AST)  $\leq$  2.5 x ULN ( $\leq$  5 x ULN for subjects with liver involvement of their cancer)
  - Alkaline phosphatase  $\leq$  2.5 x ULN ( $\leq$  5 x ULN for subjects with liver involvement of their cancer)
  - Serum creatinine  $\leq$  1.8 xULN or calculated creatinine clearance  $>45$  ml/min

- Platelet count > 50 K/mcL, hemoglobin (Hb) > 8 g/dL, absolute neutrophil count (ANC) > 1.0 K/mcL. Blood transfusion to meet the inclusion criteria will not be allowed.
- ECOG performance status 0-1 (see Appendix C).
- Subjects must be able to understand and be willing to sign the written informed consent form. A signed informed consent form must be appropriately obtained prior to the conduct of any trial-specific procedure.
- Female patients are authorized to participate if they meet the following criteria:
  - Women of child bearing potential must meet both of the following conditions:
    - Have a negative serum pregnancy test prior to enrollment and within 14 days prior to administration of the investigational product (IP).
    - Patient must use an effective form of birth control (confirmed by the Investigator) throughout the study duration and within 16 weeks after last dose of IP.
  - Female subjects who cannot bear children as evidenced by one or more of the following:
    - Bilateral Oophorectomy
    - Bilateral Salpingectomy
    - Bilateral Salpingectomy-Oophorectomy
    - Hysterectomy
    - Menopause (no menses  $\geq$  1 year prior to treatment)
    - Surgical Sterilization (i.e., tubal ligation or blockage)

**Note:** If criteria not met, patient should be regarded as having child bearing potential

- Subject must be able to receive a subcutaneous injection.
- New/worsening ercAE within 90 days prior to study enrollment. Note: This assessment will be performed by the treating investigator.

## 6.2 Participant Exclusion Criteria

- Concurrent use of another investigational drug or device for the ercAE (i.e., outside of study treatment) during, or within 4 weeks of treatment.
- Patients receiving prednisone  $\geq$  20mg a day.
- Known use of anti-IL-5 agents or biologics for the treatment of asthma which are known to decrease blood eosinophil levels.
- Patients cannot use new topicals or medications for indication of pruritus or skin rash
- Known history of anaphylaxis to biologic therapy
- A helminthic parasitic infection diagnosed within 24 weeks prior to the first treatment, that had not been treated with, or has failed to respond to, standard of care therapy.
- Known history of human immunodeficiency virus (HIV) infection or current chronic or active hepatitis B or C infection requiring treatment with antiviral therapy.
- Active infection that would impair the ability of the patient to receive study treatment.
- Women who are pregnant or breast-feeding.

- Any condition which, in the investigator's opinion, makes the subject unsuitable for trial participation.
- Receipt of live attenuated vaccines 30 days prior to the date of randomization
  - Receipt of inactive/killed vaccinations (e.g., inactive influenza) is allowed provided they were not administered within 1 week before/after any investigational product administration.
- Known history of allergy or reaction to the investigational product formulation

## 7.0 RECRUITMENT PLAN

Potential research subjects will be identified by a member of the patient's treatment team, the protocol investigator, or research team. Patient recruitment most likely will occur in the medical oncology and dermatology clinics. If the investigator is a member of the treatment team, s/he will screen their patients' medical records for suitable research study participants and discuss the study and their potential for enrolling in the research study. Potential subjects contacted by their treating physician will be referred to the investigator/research staff of the study. Investigators will discuss the study and review/sign the informed consent documents with the patient.

The principal investigator may also screen the medical records of patients with whom they do not have a treatment relationship for the limited purpose of identifying patients who would be eligible to enroll in the study and to record appropriate contact information in order to approach these patients regarding the possibility of enrolling in the study.

During the initial conversation between the investigator/research staff and the patient, the patient may be asked to provide certain health information that is necessary to the recruitment and enrollment process. The investigator/research staff may also review portions of their medical records in order to further assess eligibility. They will use the information provided by the patient and/or medical record to confirm that the patient is eligible and to contact the patient regarding study enrollment. If the patient turns out to be ineligible for the research study, the research staff will destroy all information collected on the patient during the initial conversation and medical records review, except for any information that must be maintained for screening log purposes.

In most cases, the initial contact with the prospective subject will be conducted either by the treatment team, investigator or the research staff working in consultation with the treatment team. The recruitment process outlined presents no more than minimal risk to the privacy of the patients who are screened and minimal PHI will be maintained as part of a screening log. For these reasons, we seek a (partial) limited waiver of authorization for the purposes of (1) reviewing medical records to identify potential research subjects and obtain information relevant to the enrollment process; (2) conversing with patients regarding possible enrollment; (3) handling of PHI contained within those records and provided by the potential subjects; and (4) maintaining information in a screening log of patients approached (if applicable).

### 7.1 Research Participant Registration

Confirm eligibility as defined in the section entitled Inclusion/Exclusion Criteria. Obtain informed consent, by following procedures defined in section entitled Informed Consent

Procedures. During the registration process registering individuals will be required to complete a protocol specific Eligibility Checklist. The individual signing the Eligibility Checklist is confirming whether the participant is eligible to enroll in the study. Study staff are responsible for ensuring that all institutional requirements necessary to enroll a participant to the study have been completed. See related Clinical Research Policy and Procedure #401 (Protocol Participant Registration).

## 7.2 Randomization

Not applicable

## 8.0 INFORMED CONSENT PROCEDURES

Before protocol-specified procedures are carried out, consenting professionals will explain full details of the protocol and study procedures as well as the risks involved to participants prior to their inclusion in the study. Participants will also be informed that they are free to withdraw from the study at any time. All participants must sign an IRB/PB-approved consent form indicating their consent to participate. This consent form meets the requirements of the Code of Federal Regulations and the Institutional Review Board/Privacy Board of this Center. The consent form will include the following:

1. The nature and objectives, potential risks and benefits of the intended study.
2. The length of study and the likely follow-up required.
3. Alternatives to the proposed study. (This will include available standard and investigational therapies. In addition, patients will be offered an option of supportive care for therapeutic studies.)
4. The name of the investigator(s) responsible for the protocol.
5. The right of the participant to accept or refuse study interventions/interactions and to withdraw from participation at any time.

Before any protocol-specific procedures can be carried out, the consenting professional will fully explain the aspects of patient privacy concerning research specific information. In addition to signing the IRB Informed Consent, all patients must agree to the Research Authorization component of the informed consent form.

Each participant and consenting professional will sign the consent form. The participant must receive a copy of the signed informed consent form.

## 9.0 PRE-TREATMENT/INTERVENTION

The following assessments need to be preformed within the below timelines:

Within 45 days of treatment start:

- Signed Informed Consent Form

Within 30 days of treatment start:

- Skin biopsy per SOC

Prior to registration and within 14 days of treatment start:

[figure not shown]
- Serum pregnancy test for women of child-bearing potential

On day -7 to -1:

- Medical history
- Demographics
- Physical Examination and vital signs, including heart rate, blood pressure, weight, and temperature
- Skin exam
- Concomitant medication review
- ECOG performance status
- CBC with differential
- Comprehensive Metabolic Panel, including Albumin, alkaline phosphatase, total bilirubin, bicarbonate, BUN, calcium, chloride, creatinine, glucose, potassium, total protein, SGOT[AST], SGPT[ALT], sodium
- Phosphorus

## 10.0 TREATMENT/INTERVENTION PLAN

- Benralizumab 30mg as a subcutaneous injection will be administered by a healthcare professional at once every 4 weeks for the first 3 doses (Week 0/Day 1, Week 4/Day 28, and Week 8/Day 56), followed by once every 8 weeks for 3 additional doses (Week 16/Day 112, Week 24/Day 168, and Week 32/Day 224), per the labeling instructions.

- Patients will also have a comprehensive physical examination at Week 0/Day 1
- Skin examination prior to benralizumab administration will be completed at Week 0/Day 1, Week 4/Day 28, Week 8/Day 56).

- Phlebotomy for CBC w differential at every visit (Screening, Week 0/Day 1, Week 2/Day 14, Week 4/Day 28, Week 8/Day 56, Week 16/Day 112, Week 24/Day 168, Week 32/Day 224, and 4 Weeks post-last dose).
- Total body photography at Screening, Week 0/Day 1, Week 4/Day 28, Week 8/Day 56,.
- Research blood collection for biomarker analysis (MSD Panel and IL-5) on Week 0/Day 1, Week 4/Day 28 and Week 8/Day 56:
  - Approximately 10 mL of blood will be collected in a green top sodium heparin Vacutainer tube. This sample will be sent to the Immune Monitoring Facility (IMF).
  - Approximately 4 mL of blood will be collected in a lavender top tube (with EDTA). This sample will be sent to Mayo Clinic.

**Missed doses will not be made up.**

## 11.0 EVALUATION DURING TREATMENT/INTERVENTION

Study Procedures	Screening Visit (-7 days to Day 1) 	Week 0/ Day 1	Week 2/ Day 14 (+/- 3 days)	Week 4/ Day 28 (+/- 3 days)	Week 8/ Day 56 (+/- 3 days)	Week 16/ Day 112 (+/- 7 days) 	Week 24/ Day 168 (+/- 7 days) 	Week 32/ Day 224 (+/- 7 days) 	4 Weeks post-last dose (+/- 7 days)
Informed Consent	X 								
Demographics	X								
Medical history	X								
Concomitant medication review	X	X	X	X	X	X	X	X	X
Serum pregnancy test, per SOC and if applicable	X 								
Skin biopsy 	X			X					
CBC with differential	X	X	X	X	X	X	X	X	X
Comprehensive Metabolic Panel	X								
Physical exam and vital signs (HR, BP, weight, and temperature)	X								
Skin Exam (prior to Benralizumab administration)		X		X	X				
ECOG Performance Status (Appendix C)	X								
Total body photography	X	X		X	X				
Eosinophil-related Adverse Event Grading (CTCAE v5.0) (Appendix A)	X	X	X	X	X	X	X	X	X
Research blood collection for biomarker analysis (IL-5 & MSD Panel)		X		X	X				

Adverse event evaluation	X	X	X	X	X	X	X	X	X
Patient self-assessment (PRO-CTCAE (Appendix D) & Skindex 16 (Appendix B)	X	X	X	X	X	X	X	X	X
RegiSCAR Scoring System for Diagnosing DRESS Syndrome		X							
Benralizumab 30mg SC administration		X		X	X	X	X	X	

SOC, standard of care.

1. Informed consent within 45 days prior to treatment.
2. Serum pregnancy test for WOCBP within 14 days prior to treatment.
3. The baseline skin biopsy will be obtained within 30 days of treatment start, if applicable per standard of care. The biopsy at day 28 will be RNB if the patient's symptoms are improving.
4. Assessments will continue as long as the patient continues receiving benralizumab (up to 32 weeks). If a patient discontinues benralizumab, they will move to the 4 weeks post-last dose follow-up visit.
5. Screening and Week 0/Day 1 visits can be combined as long as comprehensive metabolic panel, CBC w/ differential, and pregnancy test (if applicable) are resulted to confirm eligibility prior to first benralizumab injection.

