## 1.0 PROTOCOL SUMMARY AND/OR SCHEMA

This is a single-center, single-arm phase II study to evaluate the efficacy and safety of the anti-IL-5R $\alpha$  chimeric monoclonal antibody benralizumab for the treatment of eosinophil-related cutaneous adverse events (ercAEs) resulting from immunotherapies or targeted therapies. Forty eight (48) patients will be enrolled and the estimated time to completion is 2 years. The primary endpoint for the study is the percent reduction in CTCAE grade 2/3 eosinophil-related cutaneous adverse events to grade  $\leq 1$ . Eosinophil-related cutaneous adverse events are defined as maculopapular rash, pruritus/urticaria, bullous pemphigoid, or DRESS syndrome that are associated with blood eosinophil counts of at least .3 K/mcl. Secondary endpoints are safety and tolerability of benralizumab, calculated rash body surface area (BSA), relative dose intensity (RDI) of anticancer therapy, measurement of patient-reported quality of life, the ability to continue anticancer agents, effects on corticosteroid naïve and dependent/refractory ercAEs, the need for additional supportive care interventions (i.e. corticosteroids, antihistamines), and reduction in blood and skin eosinophils. An exploratory endpoint is analyzing eosinophils and Th2 immune pathway blood biomarkers ( IFN- $\gamma$ , IL-1 $\beta$ , IL-2, IL-4, IL-5, IL-6, IL-8, IL-10, IL-12p70, IL-13, TNF- $\alpha$ , tryptase) that correlate with benralizumab efficacy. Patients with a diagnosis of solid or hematologic cancers undergoing treatment with checkpoint inhibitors (CPIs) or targeted therapies with a grade 2/3 cutaneous adverse associated with blood eosinophil counts of at least .3 K/mcl will be treated with benralizumab 30mg once every 4 weeks for the first 3 doses (Week 0/Day 1, Week 4/Day 28, and Week 8/Day 56), followed by once every 8 weeks for 3 additional doses (Week 16/Day 112, Week 24/Day 168, and Week 32/Day 224). CTCAE v5.0 ercAE assessments will be done at baseline and then at Week 2/Day14, Week 4/Day 28, and Week 8/Day 56, Week 16/Day 112, Week 24/Day 168, Week 32/Day 224 and 4 weeks post-last dose. Patients may remain on study until ercAE progression or unacceptable toxicity from benralizumab for up to 32 weeks.

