Many of these reactions involve only the skin but some patients manifest systemic features including fever, eosinophilia, lymphadenopathy and organ dysfunction which may principally affect the liver, bone marrow and/or kidneys (Cho et al, *Int J Mol Sci* 2017). The combination of a widespread eruption with systemic dysfunction is termed DRESS (Drug Reaction with Eosinophilia and Systemic Symptoms) or DIHS (Drug-Induced Hypersensitivity Syndrome). Eosinophilia is part of the RegiSCAR diagnostic criteria for Drug Reaction with Eosinophilia and Systemic Symptoms (DRESS/DIHS). There is now the realization that patients with DRESS often develop a worsening of the clinical picture after the initial reaction starts resolving. There may be recurrence of fever, either a leukocytosis or lymphopenia and deterioration of organ function. This is due to reactivation of members of the herpes virus family, HHV6 and HHV7 in particular, but EBV and/or CMV as well. Higher eosinophil counts correlated with poor liver function, extended hospitalization, and prolonged corticosteroid use in patients with EM-type, urticaria-like, and morbilliform drug eruptions. In addition, CPI lead to eosinophil-mediated cutaneous irAE that impact QoL and ability of patients to receive life prolonging or saving therapies (Phillips et al, *J Clin Oncol* 2019).

In a broad evaluation of non-cancer inpatient adverse cutaneous drug reactions, only 18% had peripheral eosinophilia ( $>300 \times 10^6$  cells  $\text{L}^{-1}$ ). Eosinophil related cutaneous adverse events (ercAEs) have been described as a type IVb reaction, which involves a Th2-mediated immune response with secretion of IL-4, IL-13, and IL-5. IL-5 is known to be the key factor in regulating the growth, differentiation, and activation of eosinophils. Eosinophil activity is also

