The actual definition of DRESS was proposed by Bocquet *et al.* in 1996 and updated in 2007 by the Registry of Severe Cutaneous Adverse Reactions (RegiSCAR) Study Group. DRESS syndrome diagnosis is complex due to the wide variety of signs and symptoms not all present at the same time in the patient. The phenotype of the skin is imprecise; the most common presentation is polymorphous maculopapular (85%); however, monomorphic (15%), pustules (30%), and purpura (26%) also occur. Hypereosinophilia was present in 95% of cases. Other haematological manifestations were atypical lymphocytes (67%) and lymphadenopathy (54%). Internal organ involvement has been reported in 91% of cases, primarily due to hepatic injury (elevation of liver function tests or hepatomegaly). Other frequent symptoms were high fever (90%) and mild mucosal involvement (56%). The pathogenesis is unclear, but is most likely to involve several aspects, including a network of drug metabolites, specific HLA alleles, herpes viruses (EBV, HHV-6, HHV-7, or CMV), and immune system activation. Patients with high peripheral blood eosinophilia had poorer liver function, prolongation of hospitalization, and higher cumulative doses of corticosteroids. Eosinophil count in patients with an erythema multiforme-type drug eruption was associated with severe disease. In the RegiSCAR scoring system for the diagnosis of DRESS, the score increases with the degree of eosinophilia from one point if eosinophilia is between 700 and  $1499 \times 10^6$  cells  $\text{L}^{-1}$ , to two points if eosinophilia is  $\geq 1500 \times 10^6$  cells  $\text{L}^{-1}$ . The spectrum of eosinophilic drug reactions and the classes of medication associated with peripheral eosinophilia are expanding. Half (53.3%, 64/120 cases) of symptomatic eosinophilic drug reactions are potential DRESS cases, with higher numbers of cases during hospitalization than in the community. Higher eosinophil counts in patients with DRESS are significantly associated with greater impairment of liver function, prolonged hospitalization, and higher cumulative doses of corticosteroids.

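### Cheap safety improvement: liver and kidney chemistry is scheduled only at screening, so injury without symptoms has no scheduled check after dose 1

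*Combined protocol and SAP*

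**What the plan says.** Section 9.0 places the panel in the week before treatment and lists its content: "Comprehensive Metabolic Panel, including Albumin, alkaline phosphatase, total bilirubin, bicarbonate, BUN, calcium, chloride, creatinine", followed by other analytes that include AST and ALT. In the Section 11.0 table the row "Comprehensive Metabolic Panel" has one mark, under Screening. Footnote 5 gives its purpose: Screening and Day 1 may be combined provided that "comprehensive metabolic panel, CBC w/ differential, and pregnancy test (if applicable) are resulted to confirm eligibility prior to first benralizumab injection". Section 10.0 does not mention the panel. The blood work it lists is "Phlebotomy for CBC w differential at every visit" and research blood for cytokine biomarkers at Weeks 0, 4 and 8. No other section schedules liver or kidney tests on treatment.

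DRESS is part of the target condition in Section 1.0: "Eosinophil-related cutaneous adverse events are defined as maculopapular rash, pruritus/urticaria, bullous pemphigoid, or DRESS syndrome". Section 6.2 does not exclude it, and it is scored once, by RegiSCAR on Day 1. On organ involvement in DRESS, Section 3.0 says: "Internal organ involvement has been reported in 91% of cases, primarily due to hepatic injury (elevation of liver function tests or hepatomegaly". It adds that "patients with DRESS often develop a worsening of the clinical picture after the initial reaction starts resolving", and then: "There may be recurrence of fever, either a leukocytosis or lymphopenia and deterioration of organ function". Section 6.1 requires cancer patients to plan to stay on the culprit drug.

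**The concern.** The protocol describes a condition whose internal damage is mainly hepatic, can show as raised liver tests, and can worsen while the first reaction is settling. It keeps patients on the suspected drug and gives up to six doses over 32 weeks, yet it asks for liver and kidney results only once, to confirm eligibility.

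Patient safety is at stake. From dose 2 onward the investigator decides on further dosing, on delay for related toxicity (Section 15.0) and on removal (Section 12.0) with no required chemistry after screening. Section 15.0 provides for delay on non-hematologic toxicity, but the only laboratory basis it names for dose adjustment is blood counts. Entry limits also leave room for later worsening: Section 6.1 admits ALT and AST up to 2.5 x ULN (5 x ULN with liver involvement by the cancer), and creatinine up to 1.8 x ULN or a calculated clearance above 45 ml/min.

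**Working it through.** The plan states no figure on this point, so the check is a count of scheduled assessments plus the age of the only required result.

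**Inputs** (Sections 9.0, 10.0 and 11.0)
- Visits: Screening, Weeks 0, 2, 4, 8, 16, 24 and 32, and 4 weeks post-last dose, which is 9 columns.
- Doses: Weeks 0, 4, 8, 16, 24 and 32, which is 6.
- Windows: +/-3 days at Weeks 4 and 8; +/-7 days at Weeks 16, 24 and 32.
- Screening result: Day -7 to Day 1, since footnote 5 lets Screening and Day 1 be combined.

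**Coverage as planned**
- CBC is marked at 9 of 9 visits, and at 7 of 7 after the first dose.
- The panel is marked at 1 of 9 visits, and at 0 of 7 after the first dose.
- Doses with a chemistry result scheduled since the previous dose: 0 of 5 for doses 2 to 6.
- RegiSCAR is marked at 1 of 9 visits (Week 0).

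**Age of the screening result at each later dose** (youngest = earliest dose day minus 1; oldest = latest dose day plus 7)
- Dose 2, Day 28 +/-3: 25 - 1 = 24 to 31 + 7 = 38 days.
- Dose 3, Day 56 +/-3: 53 - 1 = 52 to 59 + 7 = 66 days.
- Dose 4, Day 112 +/-7: 105 - 1 = 104 to 119 + 7 = 126 days.
- Dose 5, Day 168 +/-7: 161 - 1 = 160 to 175 + 7 = 182 days.
- Dose 6, Day 224 +/-7: 217 - 1 = 216 to 231 + 7 = 238 days, about 31 to 34 weeks.

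**Under the fix**
- The panel is scheduled at 3 of the 7 visits after dose 1: Weeks 4 and 8, and 4 weeks post-last dose.
- A result from within the visit window is at most 2 x 3 = 6 days old at Weeks 4 and 8. An abstracted result at Weeks 16, 24 and 32 is at most 2 x 7 = 14 days old.
- Upper bound on added panels, if all 48 patients reach every visit and none has a usable routine result: 3 x 48 = 144. Each patient with possible DRESS adds at most 3 more, at Weeks 16, 24 and 32.

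**What cannot be derived.** The documents give no rate of silent liver or kidney injury in this population, no expected number of DRESS cases, and no frequency of routine chemistry. The number of patients affected is therefore unknown.

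**The case against.** The strongest reply is that this is a preference about monitoring intensity, and much of it stands.

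- **No drug signal.** The benralizumab reactions listed in Section 15.0 are mainly headache, pyrexia, pharyngitis, hypersensitivity and injection site reactions. No hepatic or renal toxicity is named. This stands. The case rests mainly on the condition and the culprit drug.
- **DRESS will be uncommon here.** Section 6.1 does not list it as a qualifying reaction, so such a patient would have to enter under a listed term. With organ involvement in 91% of described DRESS cases, the entry limits would turn away those with marked injury. This also stands, and leaves injury that emerges or worsens after entry.
- **Safeguards exist.** CBC with differential at every visit can show the leukocytosis or lymphopenia that Section 3.0 describes in a DRESS relapse. Adverse events are evaluated at every visit and recorded however they are found (Section 15.2). This is one centre with its own records, and routine oncology chemistry probably exists for many patients. These measures narrow the gap without closing it. None is designed to detect a silent rise in transaminases or creatinine, and general physical examination is scheduled only at Screening and Week 0. Section 14.0 collects data from other visits at the last study visit. That rule serves the final analysis and does not stop clinical review of results, but nothing requires such review before a dose.

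A reader might infer that every one of doses 2 to 6 should be conditional on a fresh panel in all patients. The documents do not support that. They give no chemistry threshold for withholding benralizumab, the Section 15.0 delay rule covers toxicity related to protocol therapy rather than DRESS from the culprit drug, and nothing places DRESS relapse as late as Weeks 16 to 32. The large age of the screening result at dose 6 describes the schedule and is not evidence of missed relapses.

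**Conclusion.** The point holds as a modest, inexpensive safety improvement. No liver or kidney chemistry is scheduled at any of the 7 visits after the first dose, so injury without symptoms, whatever its cause, has no scheduled check. The gap is confined to silent injury and probably concerns few patients.

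Two further readings would go too far. A reader might infer that chemistry will never be done on treatment; the documents show only that the protocol does not schedule it, and routine care may supply it. A reader might also infer that the efficacy result is compromised. It is not: response is a change in the CTCAE grade of the skin event (Section 13.1), and sample size, alpha and power do not depend on the panel.

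The conclusion assumes that the single mark in the table row is complete, which Section 9.0 and footnote 5 support. The judgement that the change is cheap rests on the CBC draws already scheduled; the documents give no cost.

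**What to change.** - In the Section 11.0 table, with a matching line in Section 10.0, add the Comprehensive Metabolic Panel at Weeks 4 and 8 and at 4 weeks post-last dose. Draw it with the scheduled CBC, or accept a standard-of-care result from within the visit window.
- At Weeks 16, 24 and 32, abstract the standard-of-care result. Draw the panel only if none exists for a patient flagged by the Day 1 RegiSCAR or later suspected of DRESS.
- At each dosing visit the investigator reviews the available result, grades any abnormality by CTCAE v5.0, and applies the existing rules: dose delay for related toxicity (Section 15.0), and removal for unacceptable toxicity or in the patient's best interest (Section 12.0). No new threshold is needed, and no dose has to wait for a same-day result.

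Cost: up to 144 panels, or the time to abstract results from the electronic records that Section 14.1 already uses for relative dose intensity, plus the few conditional draws and one more result to review. These visits need no extra attendance or venepuncture.
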